The biostatistician on the study team ([name]) will generate random sequence using a computer. The randomization will be in block of varying size (4 or 6) and the list will be provided to the following lead faculty who will serve as co-investigators as listed below:

Population 1: Pediatric Dentistry, [name]

Population 2: Endodontics, [name]

Population 3: General Practice, [name]

b. Allocation Concealment:

All random assignments will be placed in sequentially numbered opaque envelopes and will be handled by a staff in the respective department (not a part of the study team). If the participant is found to be eligible for the study, the resident/ student will inform the patient about the study. The team will answer all questions regarding the study and will request consent to participate in the study. After obtaining written patient consent, the department staff (not a member of the study team) will reveal the allocation.

Outcomes:

Patient important outcomes are considered including the primary outcome of completion of intended procedure without rescue anesthetic. This dichotomous outcome (success or failure of anesthesia) is linked to patients' rating of pain on a validated Heft-Parker visual analog scale. The emoji scale will be used for children. Group comparison between the articaine and Kovanaze formulations for anesthetic success will be analyzed by using Fisher's exact test.

Secondary outcomes include objective assessment of hard tissue and soft tissue anesthesia, anxiety scale (STAI-Y6 short form for children and MDAS scale for adults).

[figure not shown]
Adult participants who receive Kovanaze will also be asked to complete a survey to assess the impact of Kovanaze on patient confidence in seeking dental care.

Primary Outcome Measure in Adults:

Proportion of study participants in whom intended dental procedure could be successfully completed without the need for rescue anesthetic.

Heft Parker Scale: Each patient will rate his or her initial pain on a Heft Parker visual analogue scale, a 170-mm line with various descriptive terms. The subjects will be asked to place a mark on the scale where it best described their pain level both at the start and any time during the procedure. To interpret the data, the VAS is divided into the following four categories:

- a. No pain corresponded to 0 mm on the scale.

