The Modified Dental Anxiety Scale (MDAS) consists of 5 questions each with a 5-category rating scale, ranging from 'not anxious' to 'extremely anxious'. This answering scheme is a simplified rating system in comparison with Corah's Dental Scale that was an early 4-question measure of dental anxiety. The MDAS has an extra item about the respondent's anxiety to a local anesthetic injection that is particularly relevant for this study. (Humphris et al). Cut off is 19 or above (out of 25) for questions 1-5, which indicates a highly dentally anxious patient, possibly dentally phobic. Questions 6-8 are specific to this study to assess the effect of Kovanaze on dental anxiety.

CAN YOU TELL US HOW ANXIOUS YOU GET, IF AT ALL, WITH YOUR DENTAL VISIT BY INSERTING 'X' IN THE APPROPRIATE BOX?

- 1. If you went to your Dentist for TREATMENT TOMORROW, how would you feel?**

Not *Slightly* *Fairly* *Very* *Extremely*
Anxious *Anxious* *Anxious* *Anxious* *Anxious*

2. If you were sitting in the WAITING ROOM (waiting for treatment), how would you feel?

Not *Slightly* *Fairly* *Very* *Extremely*
Anxious *Anxious* *Anxious* *Anxious* *Anxious*

3. If you were about to have a TOOTH DRILLED, how would you feel?

Not *Slightly* *Fairly* *Very* *Extremely*
Anxious *Anxious* *Anxious* *Anxious* *Anxious*

4. If you were about to have your TEETH SCALED AND POLISHED, how would you feel?

Not *Slightly* *Fairly* *Very* *Extremely*
Anxious *Anxious* *Anxious* *Anxious* *Anxious*

5. If you were about to have a LOCAL ANAESTHETIC INJECTION in your gum, above an upper back tooth, how would you feel?

Not *Slightly* *Fairly* *Very* *Extremely*
Anxious *Anxious* *Anxious* *Anxious* *Anxious*

4. Satisfaction Questionnaire (for KOVANAZE Participants only)

These questions are to be administered at the end of the study visit to participants in Kovanaze arm only:

1. Have you ever experienced a LOCAL ANESTHETIC INJECTION in your gum, for dental treatment?

Yes No

2. When was the last time you received a LOCAL ANESTHETIC INJECTION in your gum?

> 1 year 6 months ago Less than a month ago

3. Compared to INJECTION, how effective do you think was NASAL SPRAY ANESTHETIC in reducing your anxiety and comfort during dental procedure?

Not Effective Slightly Effective No Difference Very Effective Extremely Effective

4. How likely is it that you would ask your dentist for a NASAL SPRAY ANESTHETIC, for your future treatment needs (compared to needle anesthetic)?

Never No preference Every time

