5. What is the most important deciding factor for you to choose NASAL SPRAY ANESTHETIC for your dental needs?

Cost Fear and Anxiety

6. How much extra money would you be willing pay for the NASAL SPRAY ANESTHETIC?

\$20 \$50 Up to \$100 It is not worth paying extra

7. Did your experience with the NASAL SPRAY ANESTHETIC change your outlook towards receiving future dental care?

Nothing changed; Still scared of dental visits This appointment was better but am still concerned about my future visits This appointment definitely eased my apprehension of future dental visits

8. If you had known that there was an option of NASAL SPRAY ANESTHETIC, would you have sought dental care early?

Definitely No Maybe Definitely Yes

5. Survey after 24 hours:

A short one question about the side effects of local anesthetic will be asked to the patient in person or over phone at 24 hours.

Did you suffer any of the following side-effects after your dental visit?

- nasal drainage,
- nasal congestion,
- burning,
- pressure,
- sinus congestion,
- pain and soreness at the site of the anesthesia (scored from 1-10)
- Numbing or tingling in throat
- other (Specify)_____

Flow of research study visit in adults (>18 years):

Screening of EHR will be done to identify potential study participants on a routine clinical visit. During the study visit the study related procedures would be preformed in the following order:

1. Go over the study details, answer participant questions and obtain informed consent
2. Administer MDAS anxiety survey
3. Ask patient to rate pain (if present) in the Heft Parker Scale
4. Reveal allocation (Kovanaze or Articaine)
5. Take baseline BP and heart rate
6. Administer local anesthetic
7. Wait for patient to signal achievement of meaningful anesthesia (using stop watch)
8. Map the extent of soft tissue and hard tissue anesthesia in data collection form
9. Proceed with the intended procedure
10. Assign anesthetic **failure** if subject perceives pain after start of procedure. Record the failure in data collection form and proceed with rescue anesthetic to complete the procedure
11. Assign anesthetic **success** if local anesthesia was adequate to complete the intended procedure without need for rescue anesthetic. Record in data collection form
12. Administer MDAS survey for all participants
13. Administer satisfaction questionnaire to subjects in Kovanaze group only
14. Take end of appointment BP and heart rate

Primary Outcome Measure in Children:

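### The adult survey meant to show Kovanaze's impact on confidence in seeking care goes to the Kovanaze arm only, so a changed outlook cannot be separated from the effect of the visit

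*Combined protocol and SAP*

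**What the plan says.** Specific Aims, aim 2, covers patient anxiety, tolerance and acceptability of Kovanaze. The Outcomes section adds a purpose for an adult survey: it is meant "to assess the impact of Kovanaze on patient confidence in seeking dental care".

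Three places agree on who answers it:

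- Outcomes: "Adult participants who receive Kovanaze will also be asked to complete a survey to assess the impact of Kovanaze on patient confidence in seeking dental" (the last word is cut).
- Satisfaction Questionnaire, introductory line: "These questions are to be administered at the end of the study visit to participants in Kovanaze arm only".
- Flow of research study visit in adults, step 13: "Administer satisfaction questionnaire to subjects in Kovanaze group only".

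Item 7 asks: "Did your experience with the NASAL SPRAY ANESTHETIC change your outlook towards receiving future dental care". It has three options. One says that nothing changed. The other two speak of the appointment, and the most favourable reads "This appointment definitely eased my apprehension of future dental visits".

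On rescue, step 10 of the adult visit flow says: "Record the failure in data collection form and proceed with rescue anesthetic to complete the procedure". This comes before the survey at step 13.

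The plan gives no hypothesis, test or between-arm comparison for the survey.

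**The concern.** Impact is a causal term, and a causal statement needs a comparison. The trial has randomised controls in both adult populations, but they are not asked. Any patient whose visit went well could choose a favourable option of item 7, whatever anesthetic was used. This is most plausible in Population 2, where every patient must enter with moderate to severe pain and then has the painful tooth treated.

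Rescue adds a second difficulty. A Kovanaze adult whose anesthesia fails answers the survey after the spray and a needle injection, so the answer describes both. The injection-history questions (items 1 and 2) are also asked at the end of the visit. A rescued patient could truthfully report a very recent injection because of that day's rescue.

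At stake is the interpretation of one stated secondary purpose. A high share of eased patients could be read as an effect of the spray when the design does not support that reading.

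**Working it through.** The plan gives no figure for the survey, so there is none to reproduce. The check is of who answers what and when, followed by an illustration with assumed rates.

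**1. Instruments side by side (adult visit flow and questionnaire sections)**

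| Instrument | Who | When | What it covers |
|---|---|---|---|
| MDAS | All adults | Step 2, before allocation is revealed, and step 12 | Dental anxiety |
| 24-hour question | Patients, with no restriction to one arm | 24 hours | Side effects, soreness |
| Satisfaction questionnaire | Kovanaze only | Step 13, once | Injection history, preference, payment, outlook, earlier care-seeking |

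Outlook and care-seeking appear only in the last row, which has no baseline and no control.

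The MDAS text also mentions study-specific questions 6 to 8, but only five MDAS questions are printed. Items 6 to 8 of the Kovanaze questionnaire concern payment, outlook and earlier care-seeking. The plan should state which items are meant and who answers them.

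**2. Numbers of adults**

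The sample-size section plans 45 Kovanaze and 45 articaine participants, which I read as per population. With two adult populations, 2 × 45 = 90 per arm. So 90 adults are asked and 90 are not.

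**3. What a one-arm result can show (rates assumed, not in the documents)**

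Suppose 60% of Kovanaze adults report eased apprehension. The effect of the spray is 60% minus the articaine rate:

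- articaine 10%: 60 − 10 = 50 points
- articaine 30%: 60 − 30 = 30 points
- articaine 60%: 60 − 60 = 0 points

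The 95% half-width for one arm is 1.96 × √(0.6 × 0.4 / n). It is 0.143 for n = 45 (about 46% to 74%) and 0.101 for n = 90 (about 50% to 70%). A larger sample narrows the 60% but does not tell the three cases apart.

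**4. How many answers mix spray and injection**

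The Background quotes success rates of 83% to 90%. If these applied here, 10% to 17% of 90, or about 9 to 15 Kovanaze adults, would be rescued before answering. This is an assumption, since those rates may not hold in irreversible pulpitis.

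**5. What a two-arm item 7 would give**

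Assume 30% to 70% of articaine adults report an improved outlook, and a true difference of 0 to 20 points. The half-width of the difference is 1.96 × √(p₁(1 − p₁)/n + p₂(1 − p₂)/n). Power is by the normal approximation, two-sided 0.05, for a 20-point difference.

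| n per arm | 95% half-width | Power, 20 points |
|---|---|---|
| 45 (one population) | about 16 to 21 points | about 49% to 67% |
| 90 (both pooled) | about 11 to 15 points | about 79% to 93% |

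The pooled comparison would be informative. Within one population, only a large difference would be seen reliably.

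**The case against.** The strongest reply is that this is a satisfaction questionnaire with no hypothesis attached. Preference for the spray, willingness to pay and the deciding factor make sense only for people who received it, and items 3 and 4 ask for a comparison with injection within the question itself. On this view the problem is a single word, impact, in one sentence. Much of this stands. Those items can properly stay in one arm as description, and rewording the sentence would be an acceptable minimum. It does not rescue item 7, which asks about a change and whose favourable options credit the visit.

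A second reply is that MDAS covers similar ground, before and after, in both arms. Item 7's options do overlap with anticipatory anxiety. But MDAS does not ask about outlook or confidence in seeking care, which is the purpose that the Outcomes section names.

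Third, rescue is already recorded at step 10, so answers can be split by rescue status without any design change. That stands. The split is a reporting matter, and because rescue happens after randomisation, it can only be descriptive.

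Fourth, the trial is open label, so a two-arm item 7 would still carry expectation and disappointment. That also stands. The comparison would remove the effect of the visit, not of expectation.

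A reader might infer that the survey is the only instrument for aim 2, so that the trial has no randomised answer to that aim. The documents do not support this: aim 2 includes anxiety, which MDAS measures in both arms, and the 24-hour question bears on part of tolerance without being limited to Kovanaze. Nor does the plan say that a favourable result will be attributed to the spray. That is a risk in reporting, not a planned analysis.

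**Conclusion.** The point holds for outlook and confidence in seeking care, and no further. Followed exactly, the plan gives a one-arm, single-time result that cannot identify an impact of Kovanaze on that outcome, while about 90 randomised articaine adults go unasked. The size of any misattribution is unknown. The 0-to-50-point range is an illustration with assumed response rates, and it shows only that the design does not constrain the answer. The count of 90 per arm rests on full planned enrolment and on pooling two clinically different adult populations.

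The primary outcome, the anxiety comparison and the side-effect data are unaffected. The change is worth making because it is cheap and gives a stated purpose a randomised comparison.

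**What to change.** 1. At step 13, give item 7 to adults in both arms, with the stem referring to the anesthetic received that day instead of the nasal spray. The options already speak of the appointment and can be used in either arm.
2. Compare item 7 between arms as randomised, within each adult population and pooled with stratification by population. State beforehand which options count as an improved outlook.
3. Ask items 1 and 2 of all adults once, before allocation is revealed at step 4, and remove them from step 13, so that same-day injections do not enter the history.
4. Report the Kovanaze answers by the rescue status recorded at step 10, as description only.
5. Keep items 3 to 6 and item 8 in the Kovanaze arm as descriptive acceptability data. Item 8 concerns care-seeking but is a hypothetical about the spray, so it should carry no claim of impact.
6. If the sponsor keeps the whole survey in one arm, replace the impact wording in Outcomes with a descriptive aim.

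The cost is a few short questions for about 90 more adults and a form revision, with no extra visit or staff. Expectation effects of the open-label design would remain and should be stated as a limitation.

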- Maximum blood pressure reading of 166/100 mmHg
- Vital pulp (Cold and EPT positive)

Exclusion Criteria:

- History of inadequately controlled hypertension or active thyroid disease
- Five or more nosebleeds in the past month
- Known allergy to oxymetazoline, tetracaine, benzylalcohol or para-aminobenzoic acid
- History of congenital or idiopathic methemoglobinemia
- Taking monoamine oxidase inhibitors, tricyclic antidepressants (e.g. amitriptyline), or non-selective beta adrenergic antagonists (e.g. propranolol)
- Taking oxymetazoline-containing products (i.e., Afrin) in the last 24 hours

- Pregnant and lactating women
- Non vital pulp (Cold and EPT negative)

Study Characteristics:

Design:

Randomized, open label clinical trial

Non-inferiority threshold and Sample size calculation:

The anesthetic efficiency of articaine has been reported in the literature to be around 78 – 88% (Evans et al.). The non-inferiority threshold is the maximum allowable excess of outcome events arising from the novel treatment compared with the standard treatment. The threshold for this study has been selected based on draft guidance set by the FDA (Temple et al.) and was set at 25%. Using nQuery Advisor v7.0, we verified that a sample size of 38 subjects per group would be needed to show a non-inferiority of <25% (one sided alpha of 0.05 and a power of 83%).

Accordingly, each of our study arms will have 90 subjects: 45 in Kovanaze and 45 in Articaine groups.

Accounting for screen failures and dropouts, we will recruit 100 participants in each population totaling 300 for the entire study.

Intervention:

Metered Kovanaze sprays (0.2 ml each spray, St. Renatus) in the nostril on the same side as the tooth of interest. The dose involves:

2 sprays in adult and kids weighing 40 kg or more

1 spray in kids > 6 years but weighing between > 20 kg and < 40 kg

Control:

- Children: 1.0 ml of 4% articaine (containing 1:100000 epinephrine) delivered in the periapex of the tooth of interest by labial/buccal infiltration
- Adults: 1.8ml of 4% articaine (containing 1:100000 epinephrine) delivered in the periapex of the tooth of interest by labial/buccal infiltration

Population:

Our study will evaluate the effectiveness of Kovanaze in three different populations.

Population 1: *Children (aged 6-17 years and weighing >20 kg) requiring specific procedures for treatment of oral disease*

Location: Department of Pediatric Dentistry, 3rd floor, Wood Building

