- b. Mild pain was defined as greater than 0 mm and less than or equal to 54 mm. Mild pain included the descriptors of faint, weak, and mild pain.
- c. Moderate pain was defined as greater than 54 mm and less than 114 mm.
- d. Severe pain was defined as equal to or greater than 114 mm. Severe pain included the descriptors of strong, intense, and maximum possible.

If study participants experience pain/ sensitivity/ discomfort at any time during the procedure (VAS >54), the local anesthesia would be considered a failure and rescue anesthetic (0.7 ml of articaine deposited at the periapex of the tooth of interest) administered to complete the intended procedure.

Secondary Outcome Measures in Adults:

- 1. Onset of meaningful anesthesia:** Patient will be given a stopwatch and will be instructed to press the watch at two different time points:
 - a. Onset of anesthesia (T-1 in min): Press the watch when they first perceive pain relief after the administration of local anesthetic
 - b. Significant pain relief (T-2 in min): Press the watch the second time when the patient report significant pain relief (<54 in VAS scale)

At each time of the stopwatch/ timer, the patient will record their pain in VAS scale. Treatment will proceed as long as the VAS rating is below 54mm. i.e. no to mild pain. If the pain is moderate to high at any point of the procedure (score of 54 or higher), the event would be considered anesthetic failure and a rescue anesthetic administered.

2. Spread of anesthesia:

The teeth and the soft tissues on the side of the mouth ipsilateral to the tooth of interest will be evaluated for spread of anesthesia. The number of teeth that are anesthetized will be counted after cold and electronic pulp tests and recorded (maximum possible score is 5). Similarly, the buccal and lingual gingiva will be tested for anesthesia 1 cm below the gingival margin for each of the 5 teeth ipsilateral to the tooth of interest (maximum score of 5). The hard tissue and soft tissue scores will be compared between two groups.

3. Duration and depth of anesthesia:

In addition to the initial onset, we would gather information about the depth of anesthesia (as tested by EPT and cold tests) at 15 min, 30 min and 1 hour after administration of anesthesia. This would help us identify the duration for which reliable pulpal anesthesia is maintained.

4. Anxiety in Adults:

Modified Dental Anxiety Scale (MDAS):

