2. Mild, soft verbal protest or (quiet) crying as a signal of discomfort, but does not obstruct progress. Appropriate behavior for procedure, i.e., slight start of injection, "ow" during drilling if hurting, etc.
3. Protest more prominent. Both crying and hand signals. May move head around making it hard to administer treatment. Protest more distracting and troublesome. However, child still complies with request to cooperate.
4. Protest presents real problem to dentist. Complies with demands reluctantly, requiring extra effort by dentist. Body movement.
5. Protest disrupts procedure, requires that all of the dentist's attention be directed toward the child's behavior. Compliance eventually achieved after considerable effort by dentist, but without much actual physical restraint. (May require holding child's hands or the like to start). More prominent body movement.
6. General protest, no compliance or cooperation. Physical restraint is required.

Flow of research related procedures on study visit in children:

Screening of EHR will be done to identify potential study participants on a routine clinical visit. During the study visit the study related procedures would be performed in the following order:

1. Go over the study details, answer participant questions and obtain informed consent
2. Administer STAI-Y6 questionnaire
3. Ask patient to rate pain (if present) in the Emoji Scale
4. Reveal allocation (Kovanaze or Articaine)
5. Take baseline BP and heart rate
6. Administer local anesthetic
7. Wait for patient to signal achievement of meaningful anesthesia (using stop watch)
8. Map the extent of soft tissue and hard tissue anesthesia in data collection form
9. Proceed with the intended procedure
10. Assign anesthetic **failure** if subject perceives pain after start of procedure. Record the failure in data collection form and proceed with rescue anesthetic to complete the procedure
11. Assign anesthetic **success** if local anesthesia was adequate to complete the intended procedure without need for rescue anesthetic. Record in data collection form
12. Record patient anxiety and behavior using Venham scale
13. Take end of appointment BP and heart rate

References:

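### No pain rating during the procedure is tied to a stage or prompt, and the visit flows call failure on perceived pain rather than on the score, so open-label ascertainment of the primary outcome can differ by arm

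*Combined protocol and SAP*

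**What the plan says.** The Design entry under Study Characteristics describes a "Randomized, open label clinical trial". The Outcomes section gives the primary outcome as "completion of intended procedure without rescue anesthetic" and says that this binary result "is linked to patients' rating of pain on a validated Heft-Parker visual analog scale". An emoji scale takes the place of that scale in children.

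Under Primary Outcome Measure in Adults, participants are asked to "place a mark on the scale where it best described their pain level both at the start and any time during the procedure". The children's section repeats this wording for the emoji scale. In adults, anesthesia counts as failed and rescue follows if participants "experience pain/ sensitivity/ discomfort at any time during the procedure (VAS >54" mm). The onset item under Secondary Outcome Measures in Adults asks for a VAS mark at each of two stopwatch presses, T-1 and T-2, and restates the failure rule as a score of 54 or more.

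The adult visit flow lists one pain rating, at step 3: "Ask patient to rate pain (if present) in the Heft Parker Scale". The children's flow has the counterpart: "Ask patient to rate pain (if present) in the Emoji Scale". In both flows, step 7 is the wait for meaningful anesthesia and step 9 reads "Proceed with the intended procedure". Step 10 assigns failure if the patient perceives pain after the start and moves on to rescue. Step 11 assigns success if no rescue was needed. Steps 9 to 11 mention neither a mark on the scale nor a threshold.

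**The concern.** A rule that depends on a score needs the score to be obtained while the event can happen. Permission to mark the scale at any time does not say who asks, when, or how often. One operator can ask at every stage and another can wait for a complaint, and both comply with the plan. They could classify the same patient differently.

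The mismatch between step 10 and the outcome sections adds to this. An adult who feels mild pain during drilling (above 0 and up to 54 mm) is a failure under step 10 but not under the VAS rule above 54.

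Patient and operator both know the treatment, and the plan describes no blinded assessor and no common script. Uneven asking can therefore become uneven rescue, and so uneven success rates. A participant above the threshold who is never asked and says nothing is recorded as a success, and no in-procedure score is clearly required that would show it.

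**Working it through.** **1. Occasions on which pain is rated**

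| Occasion | Source | Relation to the procedure |
|---|---|---|
| Step 3, baseline rating | Both visit flows | Before allocation and anesthetic |
| T-1 and T-2 stopwatch marks | Onset item, adults and children | After anesthetic, during the wait at step 7, before step 9 |
| Any time during the procedure | Primary outcome text, adults and children | During, but with no stage, prompt or responsible person |
| 15, 30 and 60 min | Duration and depth item, adults | Electric pulp and cold tests, not pain ratings |

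Every pain rating with a clearly defined occasion comes before the procedure.

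**2. Rules that assign failure**

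- Primary outcome text, adults: VAS above 54.
- Onset item, adults: 54 or higher.
- Primary outcome text, children: an emoji score below 4 is read as painful.
- Onset item, children: treatment proceeds below 4, and failure is above 4. This runs the opposite way.
- Step 10, both flows: perceived pain, with no score.

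These rules do not agree and must be reconciled.

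**3. The plan's own figure**

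Inputs from the sample size section are a margin of 0.25, one-sided alpha of 0.05 and power of 83%. Articaine success is quoted as 78–88%. The rates used are not stated, so I assume 78% in both arms.

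n = (1.645 + 0.954)² × 2 × 0.78 × 0.22 / 0.25² = 6.755 × 0.3432 / 0.0625 = 37.1, rounded up to 38 per group.

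This reproduces the stated 38. The point here is about ascertainment and changes no sample size.

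**4. Weight of one misclassified participant**

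1/45 = 2.2 percentage points, and 2.2/25 = 9% of the margin.

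**5. Illustration in both directions (all error rates are assumptions)**

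There are 45 per arm, and articaine success is 78–88%. The test is a one-sided 5% unpooled Wald non-inferiority test, enumerated exactly. The plan names Fisher's exact test for the group comparison; the Wald test is my stand-in because it uses the margin.

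*Missed failures.* Kovanaze is truly 25 points worse and a share m of its failures goes unrecorded. Observed Kovanaze success = 1 − (1 − p)(1 − m). For example, with p = 0.53 and m = 0.10 it is 1 − 0.47 × 0.90 = 0.577, so the observed difference is 0.78 − 0.577 = 0.203.

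| Failures missed | Chance of wrongly declaring non-inferiority |
|---|---|
| None | about 0.05 |
| 10%, Kovanaze only | about 0.12 |
| 20%, Kovanaze only | 0.23–0.26 |
| 30%, Kovanaze only | 0.40–0.45 |
| 20%, both arms | 0.14–0.17 |

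*Over-called failures.* The true rates are equal and a share e of Kovanaze successes is called failure. Observed success = p(1 − e). For example, 0.78 × 0.95 = 0.741.

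| Successes over-called, Kovanaze only | Power |
|---|---|
| None | 0.89–0.98 |
| 5% | 0.76–0.88 |
| 10% | 0.60–0.68 |

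In participants, 10% of Kovanaze failures is 0.10 × 0.47 × 45 = 2.1 down to 0.10 × 0.37 × 45 = 1.7. Similarly, 5% of successes is 0.05 × 0.78 × 45 = 1.8 up to 0.05 × 0.88 × 45 = 2.0. The first step in either table is therefore about two people in the arm.

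**The case against.** Several arguments on the other side have force.

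- **A score is implied when rescue is given.** The adult outcome text makes rescue depend on a VAS value, and participants are to be asked for marks. A reader might infer from the flows that no pain score is taken before rescue. The documents do not support that. What is absent is a scheduled rating step in the flow immediately before failure is assigned.
- **The start may mean the start of the procedure.** Initial pain is covered in the preceding sentence, so this reading is possible. It would add one defined mark, but none at a later stage.
- **The flows are summaries.** The adult flow also omits the T-1 and T-2 marks, the 15, 30 and 60 min tests and the 24-hour survey. The children's flow omits the STAI after the visit. The data collection form is not shown and may hold fields for scores. Silence in the flows is therefore weak evidence taken alone. However, the outcome sections name no in-procedure occasion either, and step 10 states a different criterion.
- **Rescue is observable in everyone.** The outcome is not missing. But rescue follows from reported pain, so uneven elicitation carries through to it.
- **The direction of bias.** It is tempting to infer a bias towards Kovanaze: the Background stresses fear of the needle, and the adult rescue is an injection. The documents do not settle this. Needle fear is not an entry criterion, adult rescue is an injection in both arms, and unblinded operators might call Kovanaze failures more readily.
- **Partial cross-check and limits of prompting.** The adult pulp tests give some independent evidence of anesthesia. A patient set on avoiding rescue can also under-mark a prompted scale.

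These arguments narrow the point. They do not remove the unscheduled rating or the conflict between step 10 and the score rules.

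**Conclusion.** The point stands as a design weakness that should be corrected. The score linked to the primary outcome has no fixed or prompted occasion during the procedure, and the visit flows apply a different criterion. In an open-label trial this lets ascertainment differ by arm in either direction.

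The firm figure is 2.2 points per misclassified participant in an arm of 45. The error and power figures are conditional illustrations: they rest on assumed error rates, mostly in one arm, and on the stand-in test. They show that about two misclassified participants would matter. They do not show that misclassification will occur, and no expected share of the margin can be given.

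**What to change.** In both visit flows, between steps 9 and 10, add pain marks (Heft-Parker or emoji) prompted with the same script at the same named procedural points in both arms, for example first drilling, deepest point and completion. For any participant given rescue without a mark having been taken, add a retrospective worst-pain mark. Rescue should not be made conditional on any mark. Record each score and its time on the data form.

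Reconcile step 10 with the score rules in the adult and children's outcome sections, and those rules with each other, so that success or failure is classified from the recorded marks by one rule. That rule should also say how to classify a participant whose mark and rescue use disagree.

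The cost is brief pauses, a few form fields and possibly a slightly lower success rate in both arms. The sample size does not change. Prompts reduce uneven elicitation but do not remove deliberate under-reporting.
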